- *Arm 2-Experimental group 2:* Intervention with written materials and demonstration videos specifically designed for this study. **This arm will evaluate the effect of a traditional, more passive form of learning, with little degree of interaction with the content.**
- *Arm 3-Experimental group 3:* Psychoeducational intervention specifically designed for this study. **With this specific intervention, participants will learn by sharing information with the session facilitator and other participants, which will facilitate a more active form of learning, with a higher degree of interaction than the previous arm.**
- *Arm 4-Experimental group 4:* Intervention using immersion 360 degrees specifically designed for this study. **Participants enrolled in this arm, by completing it, is assumed that will experience a form of learning more participatory and immersive than conventional videos, as they can interact with the content by changing the camera angle.**
- *Arm 5-Experimental group 5:* Virtual Reality intervention specifically designed for this study. **Using VR to learn procedures will encourage caregivers to learn in a fully immersive and participatory environment where they will have to interact with the virtual content, enhancing their learning experience.**
- *Arm 6-Experimental group 6:* Augmented Reality Intervention specifically designed for this study. **This intervention will increase participants' skills through active learning as they interact with real-world care situations while receiving simultaneous support from AR devices.**

In each of the experimental groups, key patient care situations will be developed and the educational solutions for each of the arms will be adapted.

The process of this phase of the study is summarized in the following **figure**.

The evaluation of the effectiveness of each of the arms will be measured, among other ways, by recording two attempts to execute the care situation to be trained in the intervention. This recording will be made at three different times: at the baseline visit (pre-intervention), after the intervention (post-intervention) and 6 months after the end of the intervention (follow-up). The control group is an exception, as there is no specific intervention and therefore the post-intervention recording is omitted. Thus, in the case of the control group, only the pre-intervention and 6 months after the intervention will be recorded.

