These recordings will be assessed by means of an objective checklist (rubric), which assesses the errors and learning on which the educational solutions have an impact. This task will be carried out by members of the research team.

Chronological development of the project

Screening visit:

Caregivers will be informed about the study, what their commitment is, what is needed from them and the requirements. Those who are interested and meet the inclusion and exclusion criteria (described in the section Inclusion/exclusion criteria and recruitment), will be asked to sign the consent form.

Subsequently, the centers will randomly assign participants to one of the study arms and construct the registration code for each caregiver, following the guidelines in the recruitment section (the caregiver's date of birth is required).

Start-up visit (Pre-intervention):

At this point, the carers will go to the medical centre to which they belong, where they will be recorded carrying out their simulated carer's work. The recording will be made using a device consisting of neutral glasses or a headband with a small camera to record comfortably. At the beginning of the recording, the caregiver's identification code must be shown. In the same session, at the end of the recording, the centres will explain to the participants that they must fill in a questionnaire with their data, the Pre-intervention Carer's Notebook, which can be accessed from a QR code/link that will be given to them at that moment.

Subsequently, the videos of the start-up sessions of each participant will be recorded and assessed by the research team with the help of staff from the centres following the rubric provided.

Intervention:

- *Intervention application (different sessions according to arm, arms 2 to 6 only).*

At this point, the corresponding intervention will be carried out for each participant. Depending on the arm to which he/she has been assigned, the procedure and duration of the intervention sessions will be different. The information for each intervention is explained in the following sections. It will follow the following scheme:

- *Arm 1 (Control group):* no specific intervention different from the natural one is performed so it will not be necessary to convene the participants of this group for this session.

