- *Arms with intervention at home (Arm 2 - Intervention with written materials and videos, Arm 4 - Intervention with 360° materials and Arm 6 - Intervention with augmented reality):* the intervention is carried out by the caregiver alone at home, so it is useful to hold a training session at the centre to explain to the caregiver the task to be carried out at home.
- *Arms with intervention at the centre (Arm 3 - psychoeducational intervention, Arm 5 - intervention with virtual reality):* the stipulated sessions of each arm will be carried out in the rooms provided in the centres.

Post-intervention visit

Once each arm's own intervention has been received, participants will be called to participate in a new recording of the care work in the medical centre. As in the pre-intervention, at the beginning of the recording, the caregiver's identification code must be shown. At the end, a new link and QR with the Post-intervention Caregiver's Notebook will be shared with them so that they can fill it in online through the link. This flow will be for all arms except for the control arm (Arm 1), where no recording will be carried out and no post-intervention caregiver's notebook will be completed.

Again, the videos resulting from the recordings of this session should be analysed following the available rubric.

Follow-up visit (+6 months)

After 6 months (follow-up phase), participants will be recorded making two attempts at the care they were trained in. As in the previous recordings, at the beginning of the recording, the caregiver's identification code must be shown. At the end, they will be given a new QR and link to the Caregiver's Notebook Follow-up.

Gold Standard (professional group)

In addition to the participants in the control and experimental groups, the study will also include a group of 10 healthcare professionals, who will act as the Gold Standard group. This group will be recorded performing all the care situations to be trained to have a standard measure with which to compare the performance of the caregivers, once they have received the training.

Data analysis

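### The plan does not say that the people scoring the rubric videos are masked to arm, which leaves the change scores open to arm-aware scoring

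*Combined protocol and SAP*

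**What the plan says.** **What is scored.** The Phase 2 text under Intervention design makes video recordings one of several effectiveness measures. Each recording holds two attempts at the care situation. "This recording will be made at three different times": baseline, after the intervention, and 6 months later. Control skips the middle one: "Thus, in the case of the control group, only the pre-intervention and 6 months after the intervention will be recorded".

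**Who scores.** Of rubric scoring in general, the same text says: "This task will be carried out by members of the research team". Under Start-up visit, the baseline videos are to be "recorded and assessed by the research team with the help of staff from the centres following the rubric provided". The Post-intervention visit text requires scoring with the rubric but names no scorer. The Follow-up visit text does not mention scoring. For those two visits only the general statement applies.

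**Who knows the arm, and when.** Under Screening visit, after consent: "Subsequently, the centers will randomly assign participants to one of the study arms and construct the registration code for each caregiver". The start-up recording comes next. For the home-based arms (2, 4 and 6), "it is useful to hold a training session at the centre to explain to the caregiver the task to be carried out at home". For arms 3 and 5, "the stipulated sessions of each arm will be carried out in the rooms provided in the centres".

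**What the video shows.** "At the beginning of the recording, the caregiver's identification code must be shown", and this is repeated for the two later visits. The Screening visit text refers to the recruitment section for how to build the code, but the recruitment text as supplied has no coding rules. Whether the code contains the arm is therefore unknown.

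**Masking.** No section mentions masking of scorers, or of anyone else.

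**The concern.** A rubric completed from video depends on human judgement. The plan describes the immersive arms in terms that expect them to teach better, so a scorer who knows the arm may lean one way without intending to. Three features make such knowledge possible: the centres hold the allocation from screening onwards, the code is on screen in every recording, and centre staff may help assess the baseline videos.

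Data analysis takes the difference between visits as the outcome. Suppose scorers favour an experimental arm by the same amount at baseline and at follow-up: the shift cancels. If they favour it more at follow-up, its improvement is inflated; if only at baseline, its improvement is understated. Neither ANOVA, Kruskal-Wallis nor the mixed model can separate such a shift from a training effect. Control has no post-intervention recording, so every randomised comparison with control rests on the baseline and 6-month scores.

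A separate issue concerns behaviour rather than scoring. The arm is assigned before the baseline recording. If caregivers are told it then (the plan does not say), their baseline performance or attendance could be affected.

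**Working it through.** The plan gives no figure for masking or scoring error, so there is nothing of its own to reproduce. The calculation below shows only how sensitive the planned comparisons are to an assumed shift.

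**Inputs**
- From the documents: 420 participants, six arms, significance at P < 0.05.
- Assumed: equal arms of 420/6 = 70 (simple randomisation does not guarantee this); two-sided tests; a net shift d (follow-up minus baseline) of 0.1, 0.2 or 0.3 SD of the analysed score in favour of an experimental arm; no true effect. A second case assumes 20% loss, which leaves 56 per arm.

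**Single experimental arm against control at 6 months**

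P(falsely better than control) = 1 − Φ(1.96 − d/√(2/n)). The standard error √(2/n) is 0.169 for n = 70 and 0.189 for n = 56.

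**Six-arm F test, all five experimental arms shifted by d**

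With control at 0 and five arms at d, the mean is 5d/6. The sum of squared deviations is (5d/6)² + 5(d/6)² = 5d²/6. Noncentrality is n·5d²/6, with 5 and 6n − 6 degrees of freedom. For n = 70 it is 0.58, 2.33 and 5.25.

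| Net shift (SD) | Contrast, n = 70 | Contrast, n = 56 | F test, n = 70 | F test, n = 56 |
|---|---|---|---|---|
| 0 | 2.5% | 2.5% | 5% | 5% |
| 0.1 | 8.6% | 7.6% | 7.7% | 7.1% |
| 0.2 | 21.9% | 18.4% | 17.6% | 14.7% |
| 0.3 | 42.7% | 35.5% | 37.6% | 30.1% |

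The zero row also covers a shift that is equal at both visits.

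**Reverse case, n = 70.** Take an assumed true effect of 0.5 SD. With no shift, power is 1 − Φ(1.96 − 0.5/0.169) = 84%. If scorers favour the experimental arm by 0.2 SD at baseline only, the apparent effect is 0.5 − 0.2 = 0.3 SD and power is 43%.

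**Volume to handle.** With no loss, five experimental arms give 350 × 3 = 1,050 sessions and control gives 70 × 2 = 140, a total of 1,190. If the two attempts are filed separately, that is up to 2 × 1,190 = 2,380 clips. The recordings of the 10 professionals are extra.

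**The case against.** The strongest reply is that the plan is silent on masking, which is not the same as choosing to score unmasked. General scoring is given to the research team, and nothing shows that its scorers hold the allocation. The rubric is described as objective, and a head-worn camera shows less of the person than a room camera would. Rubric scores are one measure among several, and nothing in the documents suggests how large a scoring shift might be. All of this stands, and it limits the point to an open risk. It does not supply masking: a checklist still needs judgement, and no masked scoring, duplicate scoring or agreement check is described.

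A reader might go further and infer three things that the text does not support.
- **That centre staff score the outcome videos knowing the arm.** Their help is mentioned only for the start-up videos, in a phrase that covers both recording and assessing, so it may mean filming. The text also does not say that the same individuals assign, deliver and score.
- **That the code reveals the arm.** It does so to anyone holding the allocation list. Whether it does so by itself cannot be told, because its content is not given.
- **That late release of the arm would mask the scoring.** Videos are assessed after the visit, so a scorer could learn the arm by then. Late release protects baseline behaviour and attendance only.

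It is also true that masking cannot be complete. Every post-intervention clip must come from arms 2 to 6.

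**Conclusion.** The point holds as an omission that leaves a real route to detection bias. Followed as written, the plan gives the centres the allocation before baseline, puts an identifying code on every clip, leaves the centre staff's part in baseline assessment unclear, and asks for no masking of whoever scores. Only a shift that differs between visits matters for comparisons between arms.

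The size is unknown. The figures of about 9%, 22% and 43% for one contrast, and 8%, 18% and 38% for the six-arm test, rest on assumed shifts of 0.1 to 0.3 SD and equal arms of 70. They show that a modest shift would matter at this sample size, not that one will occur. The change should be made before scoring starts, because masking cannot be restored once videos have been scored with the arm known.

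**What to change.** **(a) Main change: masked scoring.** State that scorers are masked to arm. Before scoring, trim the opening code, relabel the clips with random numbers and shuffle them across arms. An existing team member who does not score holds the key. This masks all six arms at baseline and 6 months. At the post-intervention visit it masks only arms 2 to 6 from each other, and the plan should say so. Mixing visits as well would protect the within-subject pre-post comparison, which a scorer who knows the visit can bias even when masked to arm. The price is that baseline and post-intervention scoring waits for the 6-month clips.

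**(b) Scorers.** Name the scorers for each visit, and say whether centre staff help with recording or with scoring. If scoring, they too see only relabelled clips.

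**(c) Separately, for baseline performance and attendance.** Assign or release the arm only after the start-up recording and the Pre-intervention Notebook are complete, using a code that does not contain the arm.

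**Cost.** No extra visits or raters. File handling covers about 1,190 participant sessions with no loss (up to about 2,380 clips if attempts are filed separately), plus the professionals' recordings if they are scored the same way. One existing team member gives up scoring to hold the key, and under (c) the arm is released one visit later.

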Title: Innovative Teaching Solutions to Improve the Outcomes of Home Caregivers

V1.01.2023

PI00868

Abstract

Justification. Caring multipathological and polymedicated patients at homes is inexorably growing in OCDE countries, with a greater risk of suffering diverse errors made by their carers. **Objective.** To promote the training of home caregivers using five different educational solutions compared against the natural intervention. **Method.** Prospective, parallel and mixed research study with two phases. *Candidates:* will be home-based caregivers caring either a person with multiple co-morbid conditions or polymedication or a person that have a permanent device implanted such as a Port-a-Cath. *First phase:* Expert groups joined together to design and plan potential educational solutions directed to caregivers based on the identification of medication and home care errors, their causes and consequences and risk factors that favor them. *Second phase:* Inter- and intrasubject single-factor experimental design (6 groups, 5 experimental groups and control, with pre-post- intervention and follow up measures), simple random assignment, to determine the effectiveness several educational solutions (n=420 participants). The study will be carried out in primary care centers and caregivers' associations in Valencian Community, Andalusia, Madrid, Murcia and Catalonia. **Expected results.** To identify critical elements for risk management in the home for caregivers. To find the most effective and optimal educational solution that also reduces the impact of gender bias in this activity.

ClinicalTrial xxxxxxxxx

Overview and aim

The increase in the number of people with chronic diseases is a significant burden of care and consumption of health care resources all over the world. Most are elderly and, in some degree, dependent for their daily activities of a caregiver. Thanks to the work of people caring people at home, these people survive while preserving their well-being as much as possible. This work covers a range of activities from physical and emotional support for the promotion of autonomy to the management of their pharmacological treatment, in many cases applying more complex care. The sex bias generally prompts that the provision of care for dependent persons is carried out by women, which widens the already existing gender gap to the detriment of women.

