The project seeks to put people at the center of interventions while respecting their digital rights. The comparison between 360V, VR, RA, web-based information, written information and standard procedure, to determine which is the best way to train home caregivers in order to increase their technical competences and soft skills, including self-confidence, is the outcome this project would analyze. This study aims to explore the

experience and needs of caregivers (skilled and unskilled) of dependent and chronically ill patients and then to design and test the effectiveness of several interventions aimed at promoting safer medication use in the home.

Methods

Intervention design

This is a prospective, parallel, fully randomized (with simple random assignment of participants to one of six arms) experimental study to compare (inter-group and intra-subject PRE and POST measures) educational interventions aimed at training caregivers using typical scenarios during their work at home in order to reduce medication and caring errors and improve caregivers' motivations and self-efficacy.

Present protocol underwent the revision and approval of an Ethics Committee Board, obtaining the approval in December 2021 and January 2023 (CODES 21/063; 22/079 and 22/080). ClinicalTrial xxxxxxxx

Recruitment

Recruitment will be carried out in the collaborating centers through the programmes for complex chronic patients, schools for carers, and associations and foundations for carers and/or diseases causing dependency situations using the "snowball" technique.

Participants (caregivers) will be recruited during a regular consultation where they go to accompany the person they care for to the consultation, or in a clinical consultation of their own where they can comment that they are caring for a person at home. Recruitment will be carried out through systematic sampling according to the list of people seen in the consultation, using $k=3$. The collaborator will systematically select 1 out of every 3 patients cited in the consultation list. If the person refuses to be included in the study, the next person on the list will be invited and then $k=3$ will be applied.

Additionally, in the recruitment of caregivers, two aspects must be considered:

- Qualification of the caregivers

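### In Arms 2-6 the later recordings are timed by receipt or end of training, and no rule keeps carers who do not complete it in the randomised comparison

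*Combined protocol and SAP*

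**What the plan says.** Allocation happens at the screening visit, after consent and before the baseline recording and any training: "the centers will randomly assign participants to one of the study arms". The design is described as "simple random assignment of participants to one of six arms", and the abstract gives the total: "to determine the effectiveness several educational solutions (n=420 participants").

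The later visits are set out as follows.

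- **Post-intervention visit, Arms 2-6.** "Once each arm's own intervention has been received, participants will be called to participate in a new recording of the care work in the medical" […].
- **Post-intervention visit, Arm 1.** Controls are exempt: this is the arm "where no recording will be carried out and no post-intervention caregiver's notebook will be completed".
- **6-month recording.** In the Phase 2 text under Intervention design it is dated "6 months after the end of the intervention (follow-up"). The Follow-up visit paragraph is looser: "After 6 months (follow-up phase), participants will be recorded making two attempts at the care they were trained in".
- **Controls.** They have no training sessions; the plan says "it will not be necessary to convene the participants of this group for this session". The Phase 2 text nevertheless counts their second recording from the intervention.

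Arms 2, 4 and 6 are delivered at home with the carer working alone. Arms 3 and 5 are delivered in sessions at the centre.

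The Data analysis section takes differences between the baseline, post-intervention and follow-up measures as outcomes. They are compared by ANOVA or Kruskal-Wallis and explored with a linear mixed effects model (LMM). It names no analysis population and no method for missing recordings.

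**The concern.** Carers are randomised before training, but in five of the six arms the outcome visits are tied to something that happens after randomisation. The plan does not define when training counts as received, and does not say what a centre does with a carer who stops attending or leaves home material unfinished. A centre that follows the text has no prompt to call that carer and no date from which to count 6 months. No control can be missed in this way.

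If those carers are not recorded, they have no difference score and fall out of the ANOVA or Kruskal-Wallis comparison. The experimental arms would then be represented by people who finished training, who may be more motivated or less burdened, and the control arm by whoever returns at 6 months. The effort of completing also differs between home and centre delivery, so the experimental arms may be filtered to different degrees. An outcome that was never recorded cannot be recovered at the analysis stage.

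**Working it through.** **Inputs.** Total 420 and six arms, from the documents. The allocation ratio is not stated; equal allocation is assumed, so 420/6 = 70 per arm. The threshold of 0.05 is from Data analysis; two-sided testing is assumed. The documents give no completion rate, outcome SD, effect size or power, so 420 cannot be reproduced and every value of p, d and ρ below is an assumption.

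**Where a bias can arise.**

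| Visit | Arms 2-6 | Arm 1 | Contrast at risk |
|---|---|---|---|
| Post-intervention | called on receipt of training | not recorded | among Arms 2-6 only |
| 6 months | dated from end of training | recorded, origin undefined | each arm against control, and among Arms 2-6 |

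**6 months, one experimental arm against control, no true effect.** Let a share p of the arm be unrecorded, and let those carers change by d SD less than the others. The recorded mean then exceeds the whole-arm mean by

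bias = p × d.

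In SD units of the change score, SE = √(1/(70(1−p)) + 1/70), and the type I error is P(|Z + bias/SE| > 1.96).

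For p = 20% and d = 0.5:

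- bias = 0.20 × 0.5 = 0.10 SD
- SE = √(1/56 + 1/70) = 0.179
- bias/SE = 0.558
- type I error = P(Z > 1.402) + P(Z < −2.518) = 0.080 + 0.006 = 8.6%

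| p | d | Bias (SD) | Type I error |
|---|---|---|---|
| any | 0 | 0 | 5% |
| 10% | 0.5 | 0.05 | 6.0% |
| 20% | 0.5 | 0.10 | 8.6% |
| 20% | 1.0 | 0.20 | 20% |
| 30% | 0.8 | 0.24 | 25% |
| 30% | 1.0 | 0.30 | 36% |

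**Second model as a check.** Suppose the share p with the lowest propensity to complete is unrecorded, and that propensity has correlation ρ with the outcome. Then bias = ρ × φ(z_p)/(1−p), with the variance of the recorded group adjusted for truncation.

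| p | ρ | Bias (SD) | Type I error |
|---|---|---|---|
| any | 0 | 0 | 5% |
| 20% | 0.2 | 0.070 | 6.8% |
| 20% | 0.3 | 0.105 | 9.1% |
| 20% | 0.5 | 0.175 | 17.1% |
| 30% | 0.5 | 0.248 | 28.3% |

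The two models agree in order of magnitude. A negative ρ gives a bias of the same size against the intervention.

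**Scale.** With 70 against 70, the difference detectable with 80% power is (1.960 + 0.842) × √(2/70) = 0.474 SD. A bias of 0.10 SD is about a fifth of that (0.10/0.474 = 0.21).

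**Among Arms 2-6.** The bias in a contrast of arms a and b is p_a d_a − p_b d_b. With d = 0.5 in both, 30% unrecorded in a and 10% in b gives 0.15 − 0.05 = 0.10 SD in favour of a. Swapping the shares reverses the sign, and equal loss cancels. The direction cannot be predicted.

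**The case against.** The best reply is that the plan describes an order of events, not an eligibility rule. The sentence on the post-intervention call stands in a chronological account that expects each participant to receive the intervention. The 6-month anchor is used for controls too, who have nothing to finish, so it looks more like a visit label than a condition. The Follow-up visit paragraph carries no completion condition. Use time is recorded and stratified on, so varying exposure was foreseen, and an LMM can use incomplete series.

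Much of this stands, and it rules out four stronger readings that a reader might infer.

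- **That the plan excludes non-completers.** No sentence says so. The risk comes from the triggers together with the absence of any instruction.
- **That all controls stay in.** Nothing supports this. Controls can be lost over 6 months by other routes, and their follow-up date is itself undefined.
- **That both later visits bias the comparison with control.** Controls have no post-intervention recording, so that comparison exists only at 6 months.
- **That the results are biased towards the interventions.** A stable difference in level between completers and others cancels in a change score. Bias requires non-completers to change less, which is plausible but not shown.

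What the reply does not supply is an instruction for the carer who does not finish. Read purely as sequence, the text still leaves that carer without a call and without a date. Stratifying by use time conditions on something that happens after randomisation and does not restore the randomised comparison. The LMM helps only if missingness depends on observed data, and its stated role is exploratory.

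**Conclusion.** The point holds as a gap that exposes the randomised comparison to selective loss, not as a demonstrated bias. The post-intervention call and the 6-month clock in Arms 2-6 both depend on training, only those arms can fail that condition, and nothing in Data analysis keeps non-completers in.

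At 6 months the likely direction is in favour of the interventions. Among Arms 2-6 the direction is unknown at either visit. Losses of 10% to 30% with a shortfall in change of 0.5 to 1.0 SD give biases of 0.05 to 0.30 SD and type I errors of 6.0% to 36%. If completion is unrelated to change, both the bias and the inflation vanish. These figures assume 70 per arm, no loss of controls and an unadjusted pairwise normal test, which is simpler than the planned analyses; they indicate scale only. The plan should be changed, because the remedy is cheap and unrecorded outcomes cannot be retrieved. Confidence is moderate, since the loss itself is inferred.

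**What to change.** In the Phase 2 text under Intervention design, and in the Post-intervention and Follow-up visit paragraphs:

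- State that every randomised participant is invited to the post-intervention recording (Arms 2-6) and the 6-month recording (all arms), whether or not training was started or completed.
- For non-completers, count from the arm's scheduled end-of-training date. For controls, set a matching follow-up date counted from baseline.
- Define when training counts as received, and record how much was done.

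In Data analysis, state that everyone is analysed in the arm to which they were randomised, using the LMM already named with all observed recordings, and that a completers-only analysis is a sensitivity analysis.

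A single fixed time from baseline for the post-intervention recording in all arms would be simpler, but session length differs by arm. It would give unequal gaps between training and recording, and could fall before a longer programme ends. The arm-specific anchor avoids this. For the same reason, one control date can match the five experimental arms only approximately.

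The cost is protocol wording, a scheduled end date for each arm, and some extra calls to non-completers for visits already planned. Estimated effects may be smaller because carers who did not finish are included.
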